11.1 TOXICITIES/SIDE EFFECTS

For adverse events (AEs) that are considered related to administration of durvalumab, the following may be applied:

- Following the first dose of durvalumab, subsequent administration of durvalumab can be modified based on toxicities observed (see **Appendix 1**). Dose reductions are not permitted.
- Treat each of the toxicities with maximum supportive care (including holding the agent suspected of causing the toxicity where required).
- If the symptoms promptly resolve with supportive care, consideration should be given to continuing the same dose of durvalumab along with appropriate continuing supportive care according to guidelines outlined in **Appendix 1**.
- If modification of durvalumab treatment is required prior to the administration of RAI, delay in giving Thyrogen and RAI therapy prior to the second dose of durvalumab is allowed if the patient remains on study.
- In addition, there are certain circumstances in which durvalumab should be permanently discontinued.
- Cycle 2 and 3 doses of durvalumab will not be held for hematologic cytopenias (leukopenia, anemia, neutropenia, thrombocytopenia), which can occur following RAI therapy.
- Re-starting of durvalumab administration after holding therapy for toxicity can be done at the investigator's discretion as long as criteria in **Appendix 1** are fulfilled. The week that durvalumab is re-started will then be considered to be Week 1. Subsequent treatments and evaluations can then be scheduled accordingly.

Based on the mechanism of action of durvalumab leading to T-cell activation and proliferation, there is the possibility of observing immune related Adverse Events (irAEs) during the conduct of this study. Potential irAEs include immune-mediated enterocolitis, dermatitis, hepatitis, and endocrinopathies. Subjects should be monitored for signs and symptoms of irAEs. In the absence of an alternate etiology (e.g., infection or PD) signs or symptoms of enterocolitis, dermatitis, hepatitis, and endocrinopathy should be considered to be immune-related.

Dose modification recommendations and toxicity management guidelines for immune-mediated reactions, for infusion-related reactions, and for non-immune-mediated reactions related to durvalumab are detailed in Appendix 1. In addition, management guidelines for adverse events of special interest (AESIs) are detailed in **Appendix 1**. All toxicities will be graded according to NCI CTCAE v4.0.

12.0 CRITERIA FOR THERAPEUTIC RESPONSE/OUTCOME ASSESSMENT

Please refer to Section 10 regarding the timing of tumor measurement assessments.

Documentation (radiologic) must be provided for patients removed from study for progressive disease (not necessary if removed based on criteria for clinical progression).

Response and progression will be evaluated in this study using the new international criteria proposed by the revised Response Evaluation Criteria in Solid Tumors (RECIST) guideline (version 1.1) [Eur J Ca 45:228-247, 2009]. Changes in the largest diameter (uni dimensional

measurement) of the tumor lesions and the shortest diameter in the case of malignant lymph nodes are used in the RECIST criteria.

12.1 Disease Parameters

Measurable disease. Measurable lesions are defined as those that can be accurately measured in at least one dimension (longest diameter to be recorded) as ≥ 20 mm by chest x-ray, as ≥ 10 mm with CT scan, or ≥ 10 mm with calipers by clinical exam. All tumor measurements must be recorded in millimeters (or decimal fractions of centimeters).

Note: Tumor lesions that are situated in a previously irradiated area are not considered measurable unless there has been demonstrated progression in the lesion.

Malignant lymph nodes. To be considered pathologically enlarged and measurable, a lymph node must be ≥ 15 mm in short axis when assessed by CT scan (CT scan slice thickness recommended to be no greater than 5 mm). At baseline and in follow-up, only the short axis will be measured and followed.

Non-measurable disease. All other lesions (or sites of disease), including small lesions (longest diameter <10 mm or pathological lymph nodes with ≥ 10 to <15 mm short axis), are considered non-measurable disease. Bone lesions, leptomeningeal disease, ascites, pleural/pericardial effusions, lymphangitis cutis/pulmonitis, inflammatory breast disease, and abdominal masses (not followed by CT or MRI), are considered as non-measurable.

Note: Cystic lesions that meet the criteria for radiographically defined simple cysts should not be considered as malignant lesions (neither measurable nor non-measurable) since they are, by definition, simple cysts.

'Cystic lesions' thought to represent cystic metastases can be considered as measurable lesions, if they meet the definition of measurability described above. However, if non-cystic lesions are present in the same patient, these are preferred for selection as target lesions.

Target lesions. All measurable lesions up to a maximum of 2 lesions per organ and 5 lesions in total, representative of all involved organs, should be identified as **target lesions** and recorded and measured at baseline. Target lesions should be selected on the basis of their size (lesions with the longest diameter), be representative of all involved organs, but in addition should be those that lend themselves to reproducible repeated measurements. It may be the case that, on occasion, the largest lesion does not lend itself to reproducible measurement in which circumstance the next largest lesion which can be measured reproducibly should be selected. A sum of the diameters (longest for non-nodal lesions, short axis for nodal lesions) for all target lesions will be calculated and reported as the baseline sum diameters. If lymph nodes are to be included in the sum, then only the short axis is added into the sum. The baseline sum diameters will be used as reference to further characterize any objective tumor regression in the measurable dimension of the disease.

Non-target lesions. All other lesions (or sites of disease) including any measurable lesions over and above the 5 target lesions should be identified as **non-target lesions** and should also be recorded at baseline. Measurements of these lesions are not required, but the

presence, absence, or in rare cases unequivocal progression of each should be noted throughout follow-up.

12.2 Methods for Evaluation of Measurable Disease

All measurements should be taken and recorded in metric notation using a ruler or calipers. All baseline evaluations should be performed as closely as possible to the beginning of treatment and never more than 4 weeks before the beginning of the treatment.

The same method of assessment and the same technique should be used to characterize each identified and reported lesion at baseline and during follow-up. Imaging-based evaluation is preferred to evaluation by clinical examination unless the lesion(s) being followed cannot be imaged but are assessable by clinical exam.

Clinical lesions: Clinical lesions will only be considered measurable when they are superficial (e.g., skin nodules and palpable lymph nodes) and ≥ 10 mm diameter as assessed using calipers (e.g., skin nodules). In the case of skin lesions, documentation by color photography, including a ruler to estimate the size of the lesion, is recommended.

Chest x-ray: Lesions on chest x-ray are acceptable as measurable lesions when they are clearly defined and surrounded by aerated lung. However, CT is preferable.

Conventional CT and MRI This guideline has defined measurability of lesions on CT scan based on the assumption that CT slice thickness is 5 mm or less. If CT scans have slice thickness greater than 5 mm, the minimum size for a measurable lesion should be twice the slice thickness. MRI is also acceptable in certain situations (e.g. for body scans).

Use of MRI remains a complex issue. MRI has excellent contrast, spatial, and temporal resolution; however, there are many image acquisition variables involved in MRI, which greatly impact image quality, lesion conspicuity, and measurement. Furthermore, the availability of MRI is variable globally. As with CT, if an MRI is performed, the technical specifications of the scanning sequences used should be optimized for the evaluation of the type and site of disease. Furthermore, as with CT, the modality used at follow-up should be the same as was used at baseline and the lesions should be measured/assessed on the same pulse sequence. It is beyond the scope of the RECIST guidelines to prescribe specific MRI pulse sequence parameters for all scanners, body parts, and diseases. Ideally, the same type of scanner should be used and the image acquisition protocol should be followed as closely as possible to prior scans. Body scans should be performed with breath-hold scanning techniques, if possible.

Ultrasound Ultrasound is not useful in assessment of lesion size and should not be used as a method of measurement. Ultrasound examinations cannot be reproduced in their entirety for independent review at a later date and, because they are operator dependent, it cannot be guaranteed that the same technique and measurements will be taken from one assessment to the next. If new lesions are identified by ultrasound in the course of the study, confirmation by CT or MRI is advised. If there is concern about radiation exposure at CT, MRI may be used instead of CT in selected instances.

Endoscopy, Laparoscopy The utilization of these techniques for objective tumor evaluation is not advised. However, such techniques may be useful to confirm complete pathological response when biopsies are obtained or to determine relapse in trials where recurrence following complete response (CR) or surgical resection is an endpoint.

Tumor markers Tumor markers alone cannot be used to assess response. If markers are initially above the upper normal limit, they must normalize for a patient to be considered in complete clinical response. Specific guidelines for both CA-125 response (in recurrent ovarian cancer) and PSA response (in recurrent prostate cancer) have been published [JNCI 96:487-488, 2004; J Clin Oncol 17, 3461-3467, 1999; J Clin Oncol 26:1148-1159, 2008]. In addition, the Gynecologic Cancer Intergroup has developed CA-125 progression criteria which are to be integrated with objective tumor assessment for use in first-line trials in ovarian cancer [JNCI 92:1534-1535, 2000].

Cytology, Histology These techniques can be used to differentiate between partial responses (PR) and complete responses (CR) in rare cases (e.g., residual lesions in tumor types, such as germ cell tumors, where known residual benign tumors can remain).

The cytological confirmation of the neoplastic origin of any effusion that appears or worsens during treatment when the measurable tumor has met criteria for response or stable disease is mandatory to differentiate between response or stable disease (an effusion may be a side effect of the treatment) and progressive disease.

12.4 Response Criteria

12.4.1 Evaluation of Target Lesions

Complete Response (CR): Disappearance of all target lesions. Any pathological lymph nodes (whether target or non-target) must have reduction in short axis to <10 mm.

Partial Response (PR): At least a 30% decrease in the sum of the diameters of target lesions, taking as reference the baseline sum diameters.

Progressive Disease (PD): At least a 20% increase in the sum of the diameters of target lesions, taking as reference the smallest sum on study (this includes the baseline sum if that is the smallest on study). In addition to the relative increase of 20%, the sum must also demonstrate an absolute increase of at least 5 mm. (Note: the appearance of one or more new lesions is also considered progressions).

Stable Disease (SD): Neither sufficient shrinkage to qualify for PR nor sufficient increase to qualify for PD, taking as reference the smallest sum diameters while on study.

12.4.2 Evaluation of Non-Target Lesions

Complete Response (CR): Disappearance of all non-target lesions and normalization of tumor marker level. All lymph nodes must be non-pathological in size (<10 mm short axis). Note: If tumor markers are initially above the upper normal limit, they must normalize for a patient to be considered in complete clinical response.

Non-CR/Non-PD: Persistence of one or more non-target lesion(s) and/or maintenance of tumor marker level above the normal limits.

Progressive Disease (PD): Appearance of one or more new lesions and/or *unequivocal progression* of existing non-target lesions. *Unequivocal progression* should not normally trump target lesion status. It must be representative of overall disease status change, not a single lesion increase.

Although a clear progression of “non-target” lesions only is exceptional, the opinion of the treating physician should prevail in such circumstances, and the progression status should be confirmed at a later time by the review panel (or Principal Investigator).

12.4.3 Evaluation of Best Overall Response

The best overall response is the best response recorded from the start of the treatment until disease progression/recurrence (taking as reference for progressive disease the smallest measurements recorded since the treatment started). The patient's best response assignment will depend on the achievement of both measurement and confirmation criteria.

For Patients with Measurable Disease (i.e., Target Disease)

Target Lesions	Non-Target Lesions	New Lesions	Overall Response	Best Overall Response when Confirmation is Required*
CR	CR	No	CR	>4 wks. Confirmation**
CR	Non-CR/Non-PD	No	PR	≥ 4 wks. Confirmation**
CR	Not evaluated	No	PR	
PR	Non-CR/Non-PD/not evaluated	No	PR	
SD	Non-CR/Non-PD/not evaluated	No	SD	Documented at least once ≥ 4 wks. from baseline**
PD	Any	Yes or No	PD	no prior SD, PR or CR

Any	PD***	Yes or No	PD	
Any	Any	Yes		
* See RECIST 1.1 manuscript for further details on what is evidence of a new lesion.				
** Only for non-randomized trials with response as primary endpoint.				
*** In exceptional circumstances, unequivocal progression in non-target lesions may be accepted as disease progression.				

Note: Patients with a global deterioration of health status requiring discontinuation of treatment without objective evidence of disease progression at that time should be reported as “symptomatic deterioration.” Every effort should be made to document the objective progression even after discontinuation of treatment.
				

For Patients with Non-Measurable Disease (i.e., Non-Target Disease)

Non-Target Lesions	New Lesions	Overall Response
CR	No	CR
Non-CR/non-PD	No	Non-CR/non-PD*
Not all evaluated	No	not evaluated
Unequivocal PD	Yes or No	PD
Any	Yes	PD
* ‘Non-CR/non-PD’ is preferred over ‘stable disease’ for non-target disease since SD is increasingly used as an endpoint for assessment of efficacy in some trials so to assign this category when no lesions can be measured is not advised		

12.4.4 Duration of Response

Duration of overall response: The duration of overall response is measured from the time measurement criteria are met for CR or PR (whichever is first recorded) until the first date that recurrent or progressive disease is objectively documented (taking as reference for progressive disease the smallest measurements recorded since the treatment started).

The duration of overall CR is measured from the time measurement criteria are first met for CR until the first date that progressive disease is objectively documented.

Duration of stable disease: Stable disease is measured from the start of the treatment until the criteria for progression are met, taking as reference the smallest measurements recorded since the treatment started, including the baseline measurements.

13.1 CRITERIA FOR REMOVAL FROM STUDY

- Disease progression.
- Development of unacceptable toxicity.
- Participants can be removed from the study at any time if the study doctor feels that it is in their best interest to do so.
- Patients may withdraw consent from the study at any time.

Treatment Beyond Progression

Given the potential for delayed responses following short periods of disease progression with immunotherapy, subjects may continue to receive therapy beyond radiographic progression if the investigator concludes that the subject is tolerating study drug and continued therapy may provide clinical benefit.

If treatment is continued beyond initial evidence of radiographic progression, study therapy should be discontinued if further evidence of progression is subsequently observed, defined as an additional 10% or greater increase in tumor burden (by RECIST v1.1 criteria) from time of initial progression (including all target lesions and new measureable lesions).

14.0 BIOSTATISTICS

The primary objective of this pilot study will be to assess the safety of administering durvalumab in combination with Thyrogen-stimulated RAI therapy in patients with recurrent/metastatic thyroid cancer. The period of dose limiting toxicity (DLT) monitoring will be 6 weeks beginning from the first durvalumab dose. Definitions for DLT are in Section 9.3. Subjects who are removed from the study for reasons other than DLT prior to the administration of the first Thyrogen injection will be replaced with another subject. Patients who do not complete the 6 week period of monitoring beginning from the first durvalumab dose for reasons other than DLT will also be replaced. If >1 of the first 3 patients, or >2 of the first 6 patients, develop DLT related to durvalumab, further accrual to the study will be halted. If this rule is not met, we plan to accrue 11 patients in total to this pilot study (see table below). All toxicities will be graded according to CTCAE v4.0.

Number of DLTs to stop in first 3 patients	Number of DLTs to stop in first 6 patients	Number of DLTs to stop in all 11 patients	Acceptable toxicity rate (H0)	Unacceptable toxicity rate (H1)	Type I error rate	Power
>1	>2	>2	0.10	0.35	0.101184466	0.80748277

Secondary objectives will be determining the best overall response rate (BOR; CRs plus PRs per RECIST v1.1 criteria) and progression-free survival (estimated using Kaplan-Meier methodology with time origin at the start of the treatment; PFS). For PFS, patients will be followed until progression of disease or death, whichever come first. Patients who continue treatment beyond initial investigator-assessed, RECIST 1.1-defined progression, and are subsequently removed from study within the

next radiographic assessment for progression, will be considered to have investigator-assessed progressive disease at the time of the initial progression event.

Exploratory objectives:

Mutation burden, neoantigen landscape, and immunoediting analysis: While the low DTC mutation burden implies a low likelihood of neoantigen formation, neoantigen analysis has never been conducted for DTC. Whole-exome sequencing data will be analyzed using the neoepitope bioinformatics pipeline developed by [name] group. Mutation calling is performed by analyzing FASTQ files with four mutation callers and filtering by allelic frequency, call quality and other empiric measures. Mutations are validated with an orthogonal next-gen sequencing panel. Candidate neoantigens are identified based on peptide sequences and predicted binding to patient-specific MHC Class I alleles. RNAseq data will be used to define a set of expressed neoepitopes and explore gene expression signatures that may correlate with response. Evolution of the mutation, neoantigen, and gene expression landscape in pre- and post-treatment samples will be analyzed to gain insights into immunoediting that may occur and infer what epitopes may be critical for efficacy. RNAseq data will also be used to explore changes in the expression of nonmutated thyroid gene expression (TG, THSR, TPO, etc...) with therapy for the same purpose. *Biostatistical analysis:* Categorical pre- and post-treatment measures will be summarized by 2-by-2 tables; continuous pre- and post-treatment measures will be summarized by mean and standard deviation of the change as well as graphical method.

Immune cell infiltrate and immunologic gene signature analysis: Tumor RNAseq data will be used to analyze changes in (a) immune cell infiltration and (b) immunologic gene signatures with therapy. First, we will estimate the relative infiltration levels of individual immune cell populations in tumor samples using two computational approaches. The first was developed by [name] and [name] at MSK which uses single set enrichment analysis (ssGSEA) to determine the abundance of T cell and other immune cell populations in the tumor microenvironment³². A related but alternative approach uses support vector regression to model cellular populations based on a reference expression matrix³³. These techniques provide efficient and accurate alternatives to flow cytometry sorting. In addition, RNAseq data permits quantification of related immunologic gene expression signatures such as IFNy signaling, granzyme B, and antigen presenting machinery genes.

Intratumor heterogeneity analysis: Recently we have developed a technique to characterize the intratumor genetic heterogeneity of tumors based on sequencing data³². Using copy number and mutational data, our computational pipeline infers subclonal populations in tumors. Here, we propose to characterize the evolution of tumors under the selective pressure of rhTSH-stimulated RAI and durvalumab treatment, and examine subclonal expansions that are associated with an immune escape phenotype, by comparing the subclonal architecture of pre- and post-treatment samples.

PBMCs: In addition to the research biopsies, peripheral blood samples will be collected serially for flow cytometry to evaluate changes in T cell subsets at different time points of therapy.

Biostatistical analysis: Proportions of T cell subsets will be summarized at each time point and plotted to reveal any trend.

cfDNA: Collected cfDNA will be analyzed to detect and quantify total cfDNA and the amounts of tumor driver oncogenes (BRAF mutations, RAS mutations, etc...) or other gene mutations present

as appropriate. *Biostatistical analysis*: Changes in these parameters that occur with therapy will be analyzed by graphical method.

Accrual to the trial is anticipated to be approximately 1 patient per month.

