9.4 Definition of Dose-Limiting Toxicity (DLTs)

The period of DLT monitoring will be 6 weeks beginning from the first durvalumab dose administered. Patients who are removed from the study for reasons other than DLT prior to the administration of the first Thyrogen injection will be replaced with another subject. Patients who do not complete the 6 week period of monitoring beginning from the first durvalumab dose for reasons other than DLT will also be replaced. Grading of DLTs will follow the guidelines provided in the Common Terminology Criteria for Adverse Events (CTCAE) version 4.0.

If >1 of the first 3 patients or >2 of the first 6 patients develop a DLT related to durvalumab, further accrual to the study will be halted. If this threshold is not crossed, 11 patients in total will be accrued to the pilot study.

With the exception of specific AEs discussed below, a DLT will be defined as any Grade 3 or higher toxicity that occurs during the DLT evaluation period felt to be possibly, probably, or definitely related to durvalumab. For >Grade 3 adverse events that occur in patients during the DLT monitoring period, investigators must use their discretion to decide if the adverse event is a DLT (e.g., alkaline phosphatase elevation in the context of known progression of hepatic and/or bone metastases might be attributed to progression of disease per investigator discretion).

Any AE requiring discontinuation of durvalumab will also be considered a DLT. Durvalumab-related AEs that occur during the 6-week DLT evaluation period and delay the administration of the second durvalumab dose and/or Thyrogen/RAI therapy by more than two weeks will also be considered DLTs.

Toxicity that is clearly and directly related to the primary disease or to another etiology is excluded from this DLT definition.

The following will be DLTs:

- Any Grade 4 immune related Adverse Event (irAE)
- Any \geq Grade 3 colitis
- Any \geq Grade 3 noninfectious pneumonitis
- Any \geq Grade 3 nephritis or renal dysfunction (elevated serum creatinine)
- Any Grade 2 pneumonitis that does not resolve to \leq Grade 1 within 3 days of the initiation of maximal supportive care
- Any Grade 3 irAE (excluding colitis, pneumonitis, thyroiditis, or nephritis) that does not downgrade to Grade 2 within 3 days after onset of the event despite optimal medical management, including systemic corticosteroids, or does not downgrade to \leq Grade 1 or baseline within 14 days

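### The DLT halting rule is worded with two limits, but the printed type I error and power need a third (>2 of all 11) that appears only in the Section 14.0 table, with no stated consequence or timing

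*Combined protocol and SAP*

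**What the plan says.** Section 14.0 (Biostatistics) gives the rule in prose: "If >1 of the first 3 patients, or >2 of the first 6 patients, develop DLT related to durvalumab, further accrual" will be halted. If the rule is not met, "we plan to accrue 11 patients in total to this pilot study (see table below". The table it points to has three limits: >1 in the first 3, >2 in the first 6, and >2 under the column headed "Number of DLTs to stop in all 11 patients". The same row gives an acceptable DLT rate of 0.10 (H0), an unacceptable rate of 0.35 (H1), a type I error of 0.101184466 and power of 0.80748277.

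Section 9.4, which defines a DLT, has only the first two limits, again with a halt to accrual as the sole consequence. For every other outcome it plans the full sample: "If this threshold is not crossed, 11 patients in total will be accrued to the pilot study". Sections 1.0 (Protocol Summary) and 4.2 (Design) have the same two limits. None of these three sections mentions the third limit or refers to the table.

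On timing, Section 9.4 says "The period of DLT monitoring will be 6 weeks beginning from the first durvalumab dose administered", and Section 14.0 expects about 1 patient per month. Patients who leave the 6-week window early "for reasons other than DLT will also be replaced".

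**The concern.** The only consequence the prose attaches to the rule is that accrual stops. Once all 11 patients are in, there is no accrual left to stop. The third limit is therefore labelled as a stopping limit, but nothing says what it stops. Nor does anything say whether it is read as soon as a third DLT is known or once after patient 11.

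Safety is the primary objective, and this is the only numeric rule attached to it; the monitoring described in Section 16.3 gives no DLT count. If the third limit is not part of the rule, the printed type I error and power describe some other rule. If it is, someone working from Section 9.4 does not know it exists, and the trial has no stated conclusion for the outcomes that cross it alone.

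**Working it through.** **Inputs.** Limits, total of 11, and rates p = 0.10 and p = 0.35, all from Section 14.0. Patients are treated as independent, and only DLT-evaluable patients are counted.

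**Method.** Split the patients into 1–3, 4–6 and 7–11, and carry forward only the paths that have not crossed a limit.

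*First 3, crossed if 2 or more DLTs:* 3p²(1−p) + p³
- p = 0.10: 0.027 + 0.001 = 0.028000
- p = 0.35: 0.238875 + 0.042875 = 0.281750

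*First 6, crossed if 3 or more, having had 0 or 1 in the first 3:* P(0 of 3)·P(3 of 3) + P(1 of 3)·P(≥2 of 3)
- p = 0.10: 0.729 × 0.001 + 0.243 × 0.028 = 0.007533
- p = 0.35: 0.274625 × 0.042875 + 0.443625 × 0.281750 = 0.136766

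*All 11, crossed if 3 or more, having crossed nothing by patient 6:* sum over counts c = 0, 1, 2 of P(c at 6, no halt) × P(≥ 3−c in the next 5)
- p = 0.10: 0.531441 × 0.00856 + 0.354294 × 0.08146 + 0.078732 × 0.40951 = 0.065651
- p = 0.35: 0.075419 × 0.235169 + 0.243661 × 0.571585 + 0.262404 × 0.883971 = 0.388967

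| Rule | p = 0.10 | p = 0.35 |
|---|---|---|
| Three limits (table) | 0.101184466 | 0.80748277 |
| Two limits (prose) | 0.028000 + 0.007533 = 0.0355 | 0.281750 + 0.136766 = 0.4185 |
| Third limit only | 0.0657 | 0.3890 |

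The three-limit totals match the printed figures to every digit. The limits at 3 and 11 alone give the same values, since more than 2 of 6 implies more than 2 of 11. The third limit supplies 0.0657/0.1012 = 65% of the printed type I error and 0.3890/0.8075 = 48% of the printed power.

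**Does timing change the printed figures?** No. A third DLT acted on at once is a third DLT by patient 11 in any case. Patient-by-patient reading gives 0.1012 and 0.8075 again.

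**Does timing change accrual?** Let c(j) be the probability that the third DLT has occurred by patient j with no halt at 3 or 6. At p = 0.35, c(7) to c(10) are 0.092, 0.181, 0.262 and 0.332. So in 33% of trials the third DLT falls at patients 7–10 and the prose keeps accruing.

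- Expected enrolment with looks at 3 and 6 only: 3 × 0.28175 + 6 × 0.136766 + 11 × 0.581484 = 8.06.
- Halting at once on the third limit saves c(7) + c(8) + c(9) + c(10) = 0.87 patients, giving 7.20.
- A 6-week window at about 1 patient per month, with no enrolment pause stated, suggests a lag of one or two patients (an assumption). The saving is then 0.54 or 0.27.
- Acting at once on a third DLT at patient 5 as well adds 0.443625 × 0.1225 = 0.05, making the savings 0.92, 0.59 and 0.33.

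At p = 0.10, halting at once raises the chance of ending accrual early from 3.6% to 3.55% + 4.76% = 8.3% (6.7% or 5.4% with a lag of one or two). Expected enrolment falls from 10.74 to 10.63.

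**The case against.** The strongest reply is that nothing conflicts. The prose says when accrual stops early, and the table column describes the final count at full accrual. The H0, H1, type I error and power labels imply that crossing the limit means judging the DLT rate unacceptable. Section 14.0 sends the reader to the table, so all three limits and the figures that belong to them stand in one section. On that reading 0.42 is the chance of an early halt, not the power of the design, and continuing to patient 11 is an ordinary consequence of fixed looks. Section 16.3 also places the trial under institutional monitoring, so accrual would not necessarily go unreviewed after a third DLT.

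Much of this stands. No printed number is wrong, the exact match shows that the third limit was in the calculation, and a final verdict after patient 11 would reconcile prose and table. The enrolment savings measure the choice of timing rather than the inconsistency.

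But the protocol nowhere states that reading. The column heading speaks of stopping, not of a verdict, and the only consequence given anywhere is a halt to accrual. Section 9.4, where the rule would be looked up during the trial, neither has the third limit nor points to it. Section 16.3 supplies no count to fill the gap.

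**Conclusion.** The concern holds. The printed 0.101 and 0.807 are correct for a three-limit rule; the rule worded in Sections 1.0, 4.2, 9.4 and 14.0 has two limits and operating characteristics of 0.036 and 0.42. The outcomes in between, 6.6% of trials at a 10% DLT rate and 39% at 35%, have no stated meaning for the primary objective.

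These probabilities are exact, given independent evaluable patients with a common DLT rate. Only the lagged enrolment figures rest on a further assumption, that one or two patients enrol before a DLT is known. This is a defect of specification, not of calculation. It should be fixed because it concerns the trial's only numeric safety rule.

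**What to change.** Reconcile Sections 1.0, 4.2, 9.4 and 14.0 with the table. Write the third limit into all four, keep the restriction to durvalumab-related DLTs, and state what crossing it means. For example: *the pre-specified criterion for an unacceptable DLT rate is met if durvalumab-related DLTs occur in more than 1 of the first 3, more than 2 of the first 6, or more than 2 of all 11 patients.* Then choose one timing:

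- (a) accrual also stops as soon as a third such DLT is known; or
- (b) the limit at 11 is a final verdict, read once after patient 11.

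The printed figures stand under both. Say that the criterion is met, not that the rate has been shown to exceed 10%: the exact (Clopper–Pearson) 95% interval for 3 of 11 is 6% to 61%. If the third limit is not intended, delete the column and restate the figures as 0.036 and 0.42.

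The cost is wording in four sections and no extra patients. Timing (a) avoids accruing after the limit is certain to be crossed. Its price is the small rise in early halts at an acceptable 10% rate shown above, and so slightly fewer patients for response, PFS and paired biopsies. Timing (b) has no such price, but does not limit accrual after a third DLT at patients 7–10.
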